#### Induction therapy

All patients will receive induction agents with basiliximab (Simulect®; Novartis Pharma B.V., Arnhem, The Netherlands) which is given as a 20 mg dose intravenously before graft reperfusion, followed by a second infusion of 20 mg on day 4 post transplantation, or intravenous antithymocyte globulin (Thymoglobulin®; Genzyme, Cambridge, MA) at an initial dosage of 1-1.5 mg/kg/day for 3 - 7 days. Two doses of 500 mg methylprednisolone will be given intravenously on day 0 and day 1 after transplantation

#### Maintenance therapy

Patients will receive a starting oral dose of mycophenolate mofetil 1 g twice daily (MMF; Cellcept®; Roche, Basel, Switzerland) or equivalent dose of mycophenolate acid EC 720 mg twice daily (MYF; Myfortic®; Novartis Pharma AG, Basel, Switzerland) based on centre practice. Steroid therapy will be initiated on day 2 with oral prednisolone 20 mg once daily for the first week, followed by weekly reduction of 2 mg until a nadir of 5 mg daily is attained. The taper schedule and corticosteroid dose may be adjusted at the discretion of the investigator (e.g. if biopsy-proven acute rejection occurs).

#### Prophylaxis against infection

All patients receive sulfamethoxazole/trimethoprim, pentamidine inhalation or other alternatives (if sulfamethoxazole/trimethoprim is contra-indicated) for Pneumocystis jirovecii pneumonia prophylaxis. Cytomegalovirus (CMV) prophylaxis with intravenous ganciclovir or oral valganciclovir will be initiated within the first 10 days post transplantation, with the duration of CMV prophylaxis (either 3 months or 6 months) depending on the donor and recipient CMV serostatus and whether antithymocyte globulin is given. Antifungal prophylaxis with nystatin will be given for 1 month post-transplant.

#### Endpoints

The primary endpoint of the study is the proportion of patients within the desired FK trough level at first steady state e.g. morning of day 3 after five unaltered FK doses and the proportion of patients within target FK levels on day 7 post initiation of FK. The FK trough level is defined as the whole blood concentration 12 h  $\pm$  15 min after the previous dose taken the night before at 8pm. Thereafter, the clinicians can change the FK dose based on the measured FK

level and/or the clinical situation of the individual patient according to routine transplant immunosuppression protocol. For the genotyping arm, the pre-specified FK target range will be 10 – 15 ng/mL in the first 1 week after transplantation and subsequently adjusted based on routine transplant immunosuppression protocol.

Secondary pharmacokinetic endpoints include

- Proportion of patients within target FK levels on day 7 post renal transplant
- Average FK level during the first 1 weeks after transplantation
- Average daily dose of FK the first 90 days post transplantation [days 3, 7, 14±3, 30±3, 60±3, 90±3 days post transplantation]
- Average concentration-to-dose ratio of FK during the first 90 days post transplantation [days 3, 7, 14±3, 30±3, 60±3, 90±3 days post transplantation]
- Time to reach the first target FK range
- Number of FK dose adjustments required to reach the target FK level
- Number of markedly sub-therapeutic FK level (defined as <4 ng/mL) and markedly supra-therapeutic FK level (defined as > 20 ng/mL)

Secondary clinical endpoints include

- Incidence of biopsy-proven acute rejection (BPAR), with histologic characteristics described accordingly to the Banff criteria [Banff 1997 scoring system with 2007 modifications] and/or clinically presumed acute rejection
- Incidence of graft loss (defined as failure to discontinue dialysis or if patient undergoes graft nephrectomy)
- Renal function at month 3 after transplantation. Estimated GFR (eGFR) will be calculated using CKDEPI equation. [Time Frame: at day 7, 14, 30±3, 60±3 and 90±3 days after transplantation ]

All patients will be followed for at least 3 months after transplantation, or until graft loss occurs (defined as death with a functioning transplant, return to dialysis or re-transplantation), whichever occurs earlier.

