### 5. STUDY DESIGN AND PROCEDURES/METHODOLOGY

#### Methodology

This is a prospective, investigator-initiated, open-label single center pilot study conducted at the Singapore General Hospital (SGH). It will compare selected end-points between a historical control group (which was dosed by mg/kg) and a prospective intervention group (which will be dosed according to genotype).

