#### Treatment/dosing:

The standard arm will comprise of historical controls who are patients who had received renal transplant from a living donor and followed up at SGH between January 2016 - December 2020 and received standard weight-based dosing of tacrolimus.

The intervention genotyping arm will comprise of patients who are scheduled to receive renal transplant from a living donor between January 2021 to January 2023. They will be assigned to receive the initial CYP3A5 genotype-based tacrolimus (FK) dose as determined by their CYP3A5 genotype:

| Likely phenotype                               | Diploypes | Initial Prograf ® dosing
(mg/kg/day given in 2 divided doses) |
|--|-----------|---|
| Extensive metabolizer
(CYP3A5 expresser)    | CYP3A*1*1 | 0.20  |
| Intermediate metabolizer
(CYP3A5 expresser) | CYP3A*1*3 |   |
| Poor metabolizer
(CYP3A5 non-expresser)     | CYP3A*3*3 | 0.15  |

The FK dose will be rounded off to the nearest 0.5 mg. FK will be administered at 8 am and 8 pm on an empty stomach.

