#### Clinical assessment

Demographic and baseline data included the age, gender, race, weight and height of the recipient, cold ischemia time, the flow panel-reactive antibody value before transplantation and at its peak, the CMV serostatus of the donor and recipient. Laboratory data — including hemoglobin level, white-cell and platelet counts, FK trough level, liver function panel, serum creatinine level and estimated glomerular filtration rate — are measured at baseline, days 0 through 7, 14±3, 30±3, 60±3 and 90±3.

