### **6.3. Safety Monitoring Plan**

The data and safety monitoring will be performed by the Principal Investigator (PI) and a team of Co-Investigators. The patient will be reviewed daily when hospitalized and will then be followed up at outpatient as per current standard of care. Data will be reviewed by the PI on a three-monthly basis and it will be stored in an encrypted device. Study will be stopped if more than 25% of the patients in the genotyping arm have a tacrolimus trough of < 3 ng/mL or > 20 ng/mL on day 3

As an additional safety precaution, the tacrolimus drug levels achieved with current protocol and the starting dose of tacrolimus will be reviewed after every 10 participants recruited. The starting dose will not deviate from the dosage recommended in the drug insert.

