## **7. DATA ANALYSIS**

### **7.1. Data Quality Assurance**

Data will be collected by investigators who are trained in the field of renal transplantation to ensure that the data is accurate, complete and reliable. For subjects in the prospective arm, the data will also be collected real-time to ensure that the information is utilized efficiently.

Data will be reviewed by the PI on a three-monthly basis. After data collection, 10% of cases will be randomly selected for review to ensure accurate and complete data collection, with an acceptable error rate of <5%

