## **8.2. Statistical and Analytical Plans**

For the analysis of efficacy, the intention-to-treat analysis will be used, which will include all patients who were treated with at least one dose of FK. Categorical variables are reported using frequency and percentages while continuous variables are expressed as medians with ranges. A chi-square statistic will be used to evaluate the null hypothesis of no difference between the standard dose group and genotype based group within the FK target range on day 3 after transplantation. Continuous data will be compared using the Mann-Whitney U test. The time to reach target FK range will be estimated with Kaplan-Meier survival analysis and compared between the groups using log-rank test. To estimate the overall effect of CYP3A5 genotype on the outcome variables of FK daily dose, FK trough concentration and dose-adjusted FK level (a measure of apparent oral clearance), a mixed between-within subjects analysis of variance will be used. This analysis will also be used to estimate the overall effect of dosing approach on renal function. All data are analysed using R Core Team (2017). A p-value < 0.05 is considered statistically significant.

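### Time to first target tacrolimus level depends on which days levels were drawn; control draw days are undocumented, and if they were sparser than in the genotype arm the log-rank test favours that arm

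*Protocol*

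**What the plan says.** Section 5 (Endpoints) lists "Time to reach the first target FK range" among the secondary pharmacokinetic endpoints. Section 8.2 fixes the method: "The time to reach target FK range will be estimated with Kaplan-Meier survival analysis and compared between the groups using log-rank test".

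Section 5 (Methodology) describes the comparison: "It will compare selected end-points between a historical control group (which was dosed by mg/kg) and a prospective intervention group". Section 5 (Treatment/dosing) describes the controls as living-donor recipients "followed up at SGH between January 2016 - December 2020 and received standard weight-based dosing of tacrolimus".

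Section 5 (Clinical assessment) says that laboratory data, including the tacrolimus trough, "are measured at baseline, days 0 through 7, 14±3, 30±3, 60±3 and 90±3". It names no arm. On data capture, Section 7.1 adds: "For subjects in the prospective arm, the data will also be collected real-time".

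Nothing in the protocol states how often controls had levels drawn, aligns draw days between cohorts, or allows for attainment falling between two draws. The numerical range is also tied to one arm: "For the genotyping arm, the pre-specified FK target range will be 10 – 15 ng/mL in the first 1 week after transplantation".

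**The concern.** Attainment can be seen only on a day when a level was drawn, and an ordinary log-rank test treats that day as the exact event time. A cohort drawn less often is affected in two ways. Patients who come into range between draws are dated to the next draw. Patients who pass through a 5 ng/mL-wide band between draws may not be counted until much later.

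The schedule in Section 5 can govern future draws, but it could not set draws already taken in 2016-2020. Control levels must come from existing records. If those records are sparser than the genotype arm's, the test compares sampling frequency as well as dosing strategy, and the error favours the intervention. A larger sample would not remove it.

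Section 2 hypothesises that the target is reached sooner, and Sections 4.1 and 8.1 say that a trend would lead to a larger study. A sampling artefact could therefore feed that decision.

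**Working it through.** **No plan figure to reproduce.** Section 8.1 gives 100 subjects with no effect size, power, event count or arm split for this endpoint. The check is a simulation in which both arms have the same level process, so every rejection is false.

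**From the protocol:** 100 patients in total; p < 0.05 (two-sided assumed); a range of 10-15 ng/mL; draws on days 0-7, 14, 30, 60 and 90.

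**Assumed, not in the protocol:** the level model and its variability; a 50 v 50 split; the range of 10-15 ng/mL applied to both cohorts throughout; all control draw patterns.

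**One-patient illustration.** A patient first in range on day 2 is dated day 2 if drawn daily, and day 3 at the earliest if drawn only on days 3 and 7.

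**Level model.** For patient i on day d, ln L = ln m + b_i·exp(−d/7) + w_id. Here b_i is normal with SD s_b, and the exponential term stands for dose adjustment. The term w_id is normal with SD s_w and day-to-day correlation ρ. For m = 10 and 12 ng/mL: s_b = 0.45, s_w = 0.20, ρ = 0.5. For m = 9 ng/mL: s_b = 0.40, s_w = 0.15, ρ = 0.7.

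**Test.** Z = Σ(d_1j − d_j·n_1j/n_j)/√ΣV_j over event days j, rejecting if |Z| > 1.96. There were 500 trials per setting, so the simulation standard error is √(0.05 × 0.95/500) ≈ 1.0 point near 5% and √(0.5 × 0.5/500) ≈ 2.2 points at mid-range.

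The genotype arm is drawn on days 1-7, 14, 30, 60 and 90. Controls are drawn on the days shown plus 14, 30, 60 and 90. Entries are false rejection rates.

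| Control draw days | m = 9 | m = 10 | m = 12 |
|---|---|---|---|
| 1-7 (same as genotype arm) | 4.2% | 4.6% | 7.0% |
| 1, 3, 5, 7 | 6.0% | 12.6% | 21.2% |
| 2, 4, 6, 8 | 13.6% | 34.0% | 51.2% |
| 3, 5, 7 | 26.4% | 67.6% | 80.8% |
| 3, 6, 9 | 24.2% | 64.6% | 84.2% |
| 3, 7 | 34.4% | 83.6% | 98.4% |

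At m = 10 with controls drawn on days 3 and 7, the average median time is 2.9 days v 7.3 days although the levels are identical. A split of 40 genotype v 60 control at m = 10 gives 5%, 15%, 38%, 64%, 69% and 86%, in the table's row order.

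**Milder gaps.** A further simulation, again with assumed SDs and medians and identical levels, used 50 v 50 and a horizon of day 7 or day 90:

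- both arms daily: 4-6%
- one control day missed: 6-9%
- controls on weekdays only or 5 of 7 days: 13-27%
- alternate days: 51-73%
- days 3 and 7 only: 94-100%

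With two or more days missed, at least 97% of the false rejections favoured the genotype arm. The two sets differ on alternate-day sampling (6-51% v 51-73%), so the size depends on the assumed level process and on which days are missed. They agree on direction, and on roughly nominal error when both cohorts are read on the same days.

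**The case against.** The strongest reply is that nothing shows controls were drawn less often. The schedule names no arm. Section 3 counts only the two genotyping tubes as additional blood, timed with regular tests, which suggests that tacrolimus draws are routine care. Controls were transplanted at the same hospital, and Section 1 describes drug monitoring as existing practice. Section 6.3 adds: "The patient will be reviewed daily when hospitalized". A reader might infer that controls were in fact sampled sparsely. The documents do not support that, and the point stands only as a condition. Equally, daily review is not a daily level, and no section states the 2016-2020 draw pattern.

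A reader might also take a false rejection rate around one half as the general size. That needs roughly half or more of the draws to be missing. With one missed day the excess is small.

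Nor is this the only endpoint bearing on earlier attainment. The primary proportions in range on days 3 and 7 test it at fixed days, and this dating mechanism does not distort them.

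Finally, Kaplan-Meier with log-rank is conventional, and details of event dating often sit in a statistical analysis plan. That is fair as to where the rule is written. But the protocol has already named the test, and the test is sound here only if draw days are comparable, which a historical control group does not ensure.

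**Conclusion.** The point holds conditionally, for a secondary endpoint in a pilot study. The controls' draw days were not set by this protocol and are not documented. If they were sparser than the genotype arm's, the planned log-rank test is biased towards earlier attainment in the genotype arm. The expected false rejection rate is about 5% if both cohorts were drawn daily, 6-9% with one missed control day, 13-27% with two missed in seven, and often 50% or more with alternate-day or sparser draws. These rates rest on assumed level distributions, arm split and draw patterns. The direction is firmer than the size. Whether any bias exists depends on a tabulation that has not been made.

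**What to change.** Amend Section 5 (Endpoints) and Section 8.2, or put the rule in the statistical analysis plan, before levels are compared:

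1. Tabulate tacrolimus draw days per patient for days 0-7 by cohort, without looking at the values, and report the table.
2. If the patterns differ, count the event in both cohorts only on common draw days, for example days 3 and 7 plus any other day available in nearly all controls.
3. For this analysis, state one target range and apply it to both cohorts.
4. As a sensitivity analysis, treat the event as interval-censored between the last out-of-range draw and the first in-range draw, with an interval-censored comparison of the cohorts. It should not be the main analysis, because levels can move in and out of range between draws.

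The cost is wording and analysis code, with no new data. Some day-level resolution is lost in the genotype arm. If both cohorts prove to have been drawn daily, the result is essentially unchanged.

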### **4.2. Criteria for Recruitment and Recruitment Process**

For the historical control group, all patients who have received living donor renal transplant between January 2016 to December 2020 at Singapore General Hospital and still currently on follow-up will be screened by the investigators to see if they meet the eligibility criteria and recruited if all criteria are met.

For the prospective group, all patients planned for a living donor renal transplant at Singapore General Hospital between January 2021 to January 2023 will be identified by the transplant coordinators and screened by the investigators to see if the subject meet the eligibility criteria and recruited if all criteria are met.

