#### Safety

The frequencies of serious adverse events which included death, graft loss, infections (including CMV and BK infection), post-transplant diabetes mellitus, neurologic events, transaminitis and acute FK-induced nephrotoxicity will be recorded. Acute FK toxicity was defined as  $\geq 15\%$  increase in serum creatinine with a return to baseline after FK dose reduction and after exclusion of other causes of renal transplant graft function deterioration.

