#### Withdrawal from study

Subjects may withdraw voluntarily from participation in the study at any time.

Possible reasons for discontinuation from the study include

- Switched out from tacrolimus to other immunosuppressants
- No longer on triple immunosuppressants either due to intolerance or infection-related complications
- Graft failure or death

If voluntary withdrawal occurs, the subject will be asked to continue scheduled evaluations, complete an end of study evaluation, and be given appropriate care under medical supervision until the symptoms of any adverse event resolve or the subject's condition becomes stable.

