## **8. SAMPLE SIZE AND STATISTICAL METHODS**

### **8.1. Determination of Sample Size**

The number of living kidney donor transplants performed at Singapore General Hospital (SGH) is low - usually between 10 to 20 kidney transplants per year. Therefore, it is unrealistic to plan for a randomized controlled study as it will take years to achieve sufficient numbers for an adequately powered study. We aim for this study to be a pilot study to determine if there is any trend in correlation between CYP3A4 genotype and dosing. If there is any trend in correlation, we can then propose to design an adequately powered and likely multi-centre study to confirm any preliminary findings from this pilot study

Thence, upon consultation with the biostatistician, it is decided that we will recruit 100 subjects who are between the ages of 21 and 75 years old and are scheduled to receive renal transplant

from a living donor and follow up at SGH between January 2016 to January 2023. The control group selected will be a historical cohort which had received tacrolimus based on weight-based dosing while the intervention group will be a prospective cohort.

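### The Endpoints section defines graft loss twice with no listed criterion in common, so as worded the secondary endpoint leaves out losses that the follow-up rule recognises

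*Protocol*

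**What the plan says.** The protocol uses the term graft loss, or a close relative, in four places.

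- **Section 5, Endpoints, secondary clinical endpoints:** "Incidence of graft loss (defined as failure to discontinue dialysis or if patient undergoes graft nephrectomy".
- **Section 5, Endpoints, closing sentence on follow-up:** the planned minimum is three months for everyone, with this alternative end: "or until graft loss occurs (defined as death with a functioning transplant, return to dialysis or re-transplantation), whichever occurs earlier".
- **Section 5, Safety:** "The frequencies of serious adverse events which included death, graft loss, infections", followed by further event types. Death and graft loss are separate items, and graft loss is not defined.
- **Section 5, Withdrawal from study:** "Graft failure or death" is one of the possible reasons for leaving the study. Again death is named apart from loss of the graft, and graft failure is not defined.

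Nothing in the protocol says that two different concepts are meant, or which definition governs where the term stands alone.

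**The concern.** One term carries two meanings within one section. The endpoint definition describes a graft that never frees the patient from dialysis, or that is removed. The follow-up definition describes a patient who dies with a working graft, goes back on dialysis, or receives another transplant. An analyst who counts exactly what the endpoint lists would leave out a graft that worked and later failed, although the same section calls that event graft loss and stops following the patient because of it.

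At stake is the meaning of the reported incidence of one of three secondary clinical endpoints, and of the graft-loss line in the safety summary. Section 2 hypothesises better clinical outcome as well as earlier target attainment, so this endpoint bears on a stated hypothesis, though not on the primary one.

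**Working it through.** The protocol states no graft-loss rate, power figure or event count, so there is no figure to reproduce. The check compares the two definitions and adds one line of arithmetic for scale.

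**Step 1. The two lists (Protocol, section 5, Endpoints).**

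| Criterion | Counts toward the endpoint | Ends follow-up as graft loss |
|---|---|---|
| Never comes off dialysis | yes | not listed |
| Graft nephrectomy | yes | not listed |
| Goes back on dialysis | not listed | yes |
| Re-transplantation | not listed | yes |
| Death with a working graft | not listed | yes |

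Criteria listed: 2 + 3 = 5. Criteria in both lists: 0.

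**Step 2. What follows for each kind of patient.**

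- *Graft works, then fails, dialysis resumes.* Follow-up ends for graft loss. The patient is in the endpoint only if the phrase about not discontinuing dialysis is stretched to cover resuming it.
- *Re-transplantation.* Follow-up ends for graft loss. This criterion alone does not put the patient in the endpoint.
- *Death with a working graft.* Follow-up ends for graft loss. The patient is not in the endpoint, but the death is recorded as its own item under Safety.
- *Never comes off dialysis, or graft nephrectomy.* The patient is in the endpoint. The follow-up sentence does not end follow-up on these criteria, although the withdrawal list allows graft failure as a reason to leave the study.

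**Step 3. Whether another section settles it.** The Safety and Withdrawal lists both name death apart from loss or failure of the graft. That sits poorly with the follow-up definition, which counts death as graft loss. Neither list gives criteria, so neither says which definition governs.

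**Step 4. Scale.** Section 8.1 gives the total: "it is decided that we will recruit 100 subjects". It does not give the split between the historical and prospective cohorts. One reclassified patient changes an incidence by 1/n:

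- both cohorts together, n = 100: 1/100 = 1.0 percentage point
- cohort of 30 (assumed): 1/30 = 3.3 points
- cohort of 50 (assumed): 1/50 = 2.0 points
- cohort of 70 (assumed): 1/70 = 1.4 points

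**Step 5. Why the handling of death matters for the comparison.** Section 4.2 takes controls who received their transplant in the earlier period "and still currently on follow-up will be screened by the investigators". A recipient who died before screening would not meet that condition, whereas a death in the prospective cohort can be observed. A definition that counts death as graft loss would therefore include a component that can hardly occur among controls.

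**The case against.** The strongest reply is that each definition is tied to its own use. Incidence is computed from the list beside the endpoint, and the end of follow-up from the list in the follow-up sentence, so each instruction can be carried out. That stands as far as it goes: the fault is one label with two meanings, not an instruction that cannot be followed. It does not explain why a loss recognised in one sentence should be absent from the count in another, and it leaves the safety item with no definition.

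A second reply is that the lists overlap clinically, because not discontinuing dialysis carries no time point and might be read to include going back on it. This also stands in part. It leaves the decision to whoever codes the event, and it does nothing for re-transplantation.

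A reader might also infer more than the documents support:

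- *That the definition changes the censoring of the other clinical endpoints.* Section 8.2 plans Kaplan-Meier and log-rank methods only for time to the FK target range. Rejection and graft loss are listed as incidences, and renal function goes into a mixed analysis of variance. No time-to-event analysis of a clinical endpoint is stated.
- *That a patient whose graft never works must stay in follow-up.* The withdrawal list lets graft failure end participation.
- *That deaths with a working graft go unreported.* Death is its own item under Safety.
- *That the two cohorts will be coded under different versions.* The endpoint definition is not specific to a cohort. Different coding of past records and prospective data is possible, but nothing in the protocol indicates it.
- *That the choice decides whether a cohort shows any graft loss at all.* That needs an expected number of losses, and the protocol gives none.

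**Conclusion.** The inconsistency is real and can be seen within one section of the current text: two definitions of graft loss, none of five criteria shared, and a third use with no definition. As worded, the endpoint omits re-transplantation and, unless read broadly, return to dialysis after initial function, both of which the protocol itself calls graft loss.

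The reach is limited. One secondary endpoint of a pilot study and one safety item are affected. The primary endpoint and the sample size are not, nor is the day 3 stopping rule in section 6.3. The size is 1 percentage point per reclassified patient over all 100 subjects, or 3.3 to 1.4 points within a cohort of 30 to 70. That range is an assumption, because the split is not stated. How many patients would be reclassified cannot be derived from the protocol. The point deserves correction before events are coded, but it does not threaten the main comparison.

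**What to change.** Reconcile the places where the term is used. Write one definition of graft loss and refer to it in the secondary endpoint, the follow-up rule and the safety list. It should cover never coming off dialysis, going back on dialysis, graft nephrectomy and re-transplantation. Report death with a working graft separately, in line with the Safety and Withdrawal lists. If death is still meant to end follow-up, name it there as its own event and not as a form of graft loss. State that the definition applies identically to the historical and the prospective cohort.

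The cost is a short text amendment and a matching entry on the data collection form. That form (Appendix 4) is not shown, so it is likely but unconfirmed that its existing fields already capture every component.
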